# As EndoNET is a Type A trial, under HRA/MHRA guidance (https://s3.eu-west-2.amazonaws.com/www.hra.nhs.uk/media/documents/hra-mhra-econsent-statement-sept-18.pdf),

patients using e-consent in person or clinic will be required to provide a simple electronic signature in the form of a handwritten signature using a finger or a stylus on their tablet, mobile phone or other electronic device. It is also possible to sign the consent form using a computer and web-browser, provided the patient has access to the internet. If patients are unable to use the internet or do not have access to an email address, paper-based methods will be sought. The electronic consent form will include a participant dated signature and will be counter-signed by the individual who has been delegated the responsibility of confirming the consent.

The paper consent form (if requested by the patient) will include a participant dated signature and dated name of the person who presented and obtained the Consent. The person who obtains the consent must be suitably qualified and experienced and have been authorised to take consent by the site's Principal Investigator. If electronic consent or electronic remote consent is obtained, a copy of the signed Consent

EndoNET\_Protocol\_V4.0\_21Aug2024

© Copyright: The University of Oxford and Oxford University Hospitals NHS Foundation Trust 2022 Page 44 of 84 Form will be emailed securely via the trial's own instance of REDCap as a PDF to the participant (or a printed version provided if requested), a copy placed in the medical notes, and the original will be retained securely on REDCap.

## 9.5.1. QRI consent process

## a. QRI consent processes for TMG members and recruiters

TMG members and recruiters (defined above) will be invited to take part in a QRI interview and/or audiorecording of recruitment appointments, as is appropriate to their role. Individuals will be informed about the QRI study processes via a single QRI information sheet, which will be disseminated at Site Initiation Visits (if conducted in person) or via email. The information sheet will explain the QRI processes described above (specifically, interviews and audio-recording of recruitment consultations). Research nurses or the QRI researcher will obtain written consent from TMG members/recruiters using a 'QRI consent form for health care professionals and research personnel', which will seek permission for each of the individual QRI elements described above. Potential participants may opt to participate in just one, both, or neither of the QRI activities.

If infection transmission mitigation strategies are in place (e.g. during the Covid-19 pandemic) at the time of data collection, we will employ a remote consent process. Potential participants will be sent a copy of the study information sheet and consent form via email. The QRI researcher will call the HCP or research personnel and read each statement on the 'QRI consent form for health care professionals and research personnel', initial these as the HCP or RP responds in the affirmative, and sign to confirm consent has been obtained. All QRI consent forms will be sent to and/or retained at sites.

## b. QRI consent processes for patients

The dedicated QRI PIS explains the QRI study processes: specifically, the audio-recording of recruitment discussions and the possibility of patients being approached for an interview. We will employ a two-step consent process for audio-recording recruitment discussions. In brief:

- Audio-recording of consultations will only proceed if the TMG member/recruiter has also provided consent. A health care professional or research personnel will obtain verbal consent to record the initial discussion about EndoNET. If the patient agrees, the professional will record the outcome on the QRI consent form and sign to document that verbal consent has been obtained, and the discussion will be audio-recorded. This is necessary, given the intention to capture how the RCT is introduced to and received by patients.
- Patients will receive the PIS in the above clinic visit and will be provided sufficient time to ask any questions and consider their participation in the QRI.
- A healthcare professional or research personnel will obtain informed consent for the QRI study during a subsequent visit or remote discussion, using the dedicated QRI consent form. The consent form will include individual clauses relating to use of audio-recorded consultations, and the possibility of being contacted for a future interview to discuss how patients reached their decision about RCT participation. If informed consent for the audio-recording of consultations is obtained, the recordings will be sent to the QRI team. If consent is not obtained, any recordings already collected will be deleted.

EndoNET\_Protocol\_V4.0\_21Aug2024

© Copyright: The University of Oxford and Oxford University Hospitals NHS Foundation Trust 2022 Page 45 of 84 Patients may accept or decline participation in the audio-recordings, interviews, or both elements of the QRI study. They will be informed that their decision about QRI participation will have no bearing on their decision about RCT participation, and that patients may participate in the QRI if they have declined the RCT participation. Informed consent for the different elements of the QRI (i.e. audio recording consultations and interviews) will be recorded on the dedicated QRI ('Information Study') consent form.

## 9.5.2. Nested Qualitive Study (NQS) Consent

Participants in the main trial are asked if they are willing to be contacted about taking part in future research. Of those participants indicating a willingness to be contacted, the University of Oxford's instance of REDCap will automatically send an email to the NQS researcher to notify them when a participant has been randomised into the trial.

The NQS researcher at the University of Southampton will login to REDCap or the Study Information Management System (SIMS) to view pseudonymised data including: screening ID number, age category (for example <60 years old), randomisation outcome and recruiting hospital, baseline surgical plan (BCS vs. mastectomy) and nodal status. Potential participants will then be purposefully selected based on selective sampling criteria and the NQS researcher at the University of Southampton will ask the central trial team at the University of Oxford to provide that potential participant with a copy of the NQS invitation letter or email, NQS information sheet, copy of the ICF and reply slip/envelope.

If potential participants are interested in learning more about the NQS and are considering taking part, they can return the reply slip to the University of Southampton using the freepost envelope provided. If they do not want to take part, the reply slip contains an option to indicate they are not interested in participating. The reply slip also indicates that they can contact the researcher by phone/email instead to provide their response. If potential participants do not return the reply slip, they will be contacted by the University of Oxford by phone/email to check if they are interested in the study. If they are interested, they will be given the contact details of the University of Southampton team and be asked to contact them directly. If they do not want to take part, no further communication will be made.

The potential participant will be given sufficient time to consider the information and the NQS researcher at the University of Southampton will call the potential participant usually within 7 days. This will provide sufficient time for the patient to review the NQS information further, whilst also enabling the first interviews to take place as soon as possible after they have started their endocrine therapy. Potential participants will be given the opportunity to ask any questions that may have arisen from the written materials and will be asked if they would like to take part. The NQS researcher will then arrange a date to consent the patient and conduct the first interview, ensuring that they have received a copy of the invitation pack in advance.

Only a small number of main trial participants will be contacted and only those who have indicated a willingness to be contacted about future research will be asked about the NQS. In order to minimise fatigue for those women who do not use a reply slip, the follow up phone call to potential participants by the University of Oxford will be kept short and it will be established quickly whether they are happy to hear more information on the NQS and if they have already responded to the University of Southampton. It is necessary to follow up with participants promptly after the invitation letter, rather than solely relying on

EndoNET\_Protocol\_V4.0\_21Aug2024

© Copyright: The University of Oxford and Oxford University Hospitals NHS Foundation Trust 2022 Page 46 of 84 participants contacting the central trial team using a reply slip, to ensure discussion of the NQS occurs in a timely manner after the receipt of the information. It is important for interviews to take place promptly after randomisation as the integrity of the qualitative interviews and their findings depends on talking to women who have recently started their hormone treatment and before any side effects have developed.

The NQS researcher will call the potential participant on the agreed date using their preferred method, either by telephone or videoconferencing (Microsoft Teams). Verbal consent (audio-recorded on an Olympus DS-9000 audio recorder with encryption) will be obtained by the NQS researcher reading out each statement on the consent form to the patient. The participant will say "yes" to each statement if in agreement, with the researcher recording the outcome on the consent form before the interview starting. The researcher will sign and date the consent form to conclude the consent process. The audiorecorded consent and original version of the ICF will be stored securely at the University of Southampton and a copy of the ICF will be sent securely to the participant by post or email.

## 9.6. Randomisation (Main Trial)

We will randomise eligible patients using the centralised validated computer randomisation program through a secure (encrypted) web-based service, RRAMP (https://rramp.octru.ox.ac.uk), provided by the Oxford Clinical Trials Research Unit (OCTRU), accessed via the study's REDCap instance, with a minimisation algorithm to ensure balanced allocation across treatment arms, stratified in a 1:1 ratio to either NET followed by standard of care or standard of care using:

- Age group (<60, 60-70, 70+ years);
- Nodal status (N0 vs N1 or N2);
- Recruiting centre, and
- Surgical indication at baseline (BCS vs mastectomy)

To ensure the unpredictability of treatment allocation the minimisation algorithm will include a probabilistic element and a small number of participants randomised by simple randomisation. Stratification by centre will help to ensure that any centre-effect will be equally distributed in the trial arms and enable practical issues associated with the active intervention to be overcome. In the unlikely event that the randomisation system is down for any reason, if delays in randomisation occur to such an extent that they impact treatment planning felt to affect the prognosis of the participant, then they will be withdrawn and returned to the usual standard of care pathway if deemed necessary by the treating clinician. For participants who do not wish to or who are unable to comply with their randomisation outcome (according to the investigator and/or clinical team), they will continue to participate in the study but will be analysed on an intention to treat basis.

## 9.7. Blinding and code-breaking

Due to the nature of the intervention, it is not possible to blind individuals for the purpose of the trial. However, a pre-specified statistical analysis plan will be written in advance of un-blinding the data and any comparative analyses.

EndoNET\_Protocol\_V4.0\_21Aug2024

© Copyright: The University of Oxford and Oxford University Hospitals NHS Foundation Trust 2022 Page 47 of 84

## 9.8. Baseline Assessments (Main Trial)

Case Report Forms (CRF) will include collection of routine clinical data including patient and tumour characteristics, co-morbidity (using the Charlson Comorbidity Index) and cancer treatments and progress through treatment pathway. This information will be collected as required to describe the cohort and assess the representativeness of those recruited within the study to the general breast cancer population. It will also be used to explore for association and relationships between variables and to control for potential confounders.

The information will be recorded on the web-based form (which goes straight into the password protected study database) by the attending clinician or delegate including a member of the research team and in addition to routine clinical data, patient and tumour characteristics will also include:

- Ethnicity
- BMI (height/weight)
- Family history of breast cancer (first degree relatives only)
- Major comorbidity and medical history
- Questionnaire preference (email/post).

## 9.9. Trial imaging (Main Trial)

## 9.9.1. Imaging for trial purposes

USS +/- breast MRI, are used in most centres to monitor response to preoperative neo-adjuvant treatment. In the NET arm USS is required 2-4 weeks after start of treatment in order to place the marker clip and take core biopsies for Ki67 measurements. USS is then required at 3 and 5 months to evaluate any possible tumour response to the AI. If a patient has dense breasts or a discrepancy between mammography and USS size estimates a baseline MRI is undertaken to assess disease extent. If local policy, the participant may have MRI at the follow up timepoints (e.g. at 3 and/or 5 months) to correspond to the USS evaluation. If breast MRI is standard practice for neo-adjuvant treatment at a centre then this may be used in this trial, in addition to USS.

Baseline USS examination should include examination of the whole breast to assess disease extent. The tumour is measured in at least two dimensions (usually perpendicular to each other) and documented in millimetres with the accurate position of the probe recorded and images archived to improve interobserver accuracy. In line with standard practice, the maximum tumour diameter will be recorded and used to assess tumour response using RECIST 1.1 criteria (102). It is advised that for the 3 and 5 month USS in the NET arm, that the radiologist should review any previous image(s) in order to try and replicate the same measurement planes to minimise the subjective bias in USS. It is also recommended that USS images are captured in both planes. This will also allow for use in future research.

The axilla should be assessed carefully prior to entry to the trial by USS (as per national guidelines for all patients with invasive breast cancer) with any abnormal nodes biopsied by core biopsy or fine needle aspiration cytology (FNAC). The number of abnormal nodes should be recorded and documented. USS guided core biopsy and marker clip insertion is undertaken at 2-4 weeks. Prior to biopsy the tumour size is measured taking care to use the same positioning as the baseline examination.

EndoNET\_Protocol\_V4.0\_21Aug2024

© Copyright: The University of Oxford and Oxford University Hospitals NHS Foundation Trust 2022 Page 48 of 84 MRI examinations if undertaken should follow local protocol.

#### 9.9.2. Imaging for standard of care

Baseline USS examination should include examination of the whole breast to assess disease extent. The tumour is measured in at least two dimensions (usually perpendicular to each other) and documented in millimetres with the accurate position of the probe recorded and images archived to improve interobserver accuracy. In line with standard practice, the maximum tumour diameter will be recorded and used to assess tumour response using RECIST 1.1 criteria (102).

The axilla should be assessed carefully prior to entry to the trial by USS (as per national guidelines for all patients with invasive breast cancer) with any abnormal nodes biopsied by core biopsy or fine needle aspiration cytology (FNAC). The number of abnormal nodes should be recorded and documented.

If a patient has dense breasts or a discrepancy between mammography and USS size estimates a preoperative MRI is undertaken to assess disease extent. Any additional disease which would alter planned surgical procedure should be biopsied to confirm the abnormality is indeed malignant.

MRI examinations can be undertaken at 1.5T or 3T machines. T2W, Pre and post contrast sequences are undertaken at minute intervals up to 6 minutes with a pixel size of less than 2 mm x 2mm and slice thickness of 2 mm. Diffusion weighted imaging is undertaken with b values of 60 and 800 so that ADC can be calculated. The entire examination should be less than 30 minutes in length while aiming to achieve highest resolution imaging with good temporal dynamic post contrast imaging.

## 9.10. Surgical treatment (Main Trial)

Since surgical treatments constitute the primary endpoint, and several of the secondary endpoints, these will be recorded in detail within the CRFs. Surgery to the breast will be mastectomy or breast conservation according to local protocols, national guidance and surgeon and patient agreement. Immediate breast reconstruction and oncoplastic procedures will also be performed as appropriate. Following breast conservation clear margins should be obtained. Margin involvement will be according to local and national protocols and if margins are considered involved re-excision should be performed.

Surgery to the axilla will also be according to local protocols, national guidance and surgeon and patient agreement. Sentinel node biopsy (SNB) should be performed where pre-operative staging indicate no axillary node involvement. Where axillary node involvement is confirmed pre-operatively SNB or axillary dissection is acceptable according to the clinical situation and local and national guidance. In the NET arm clip placement or others forms of localisation of axillary nodes confirmed to be involved pre-NET is acceptable according to local protocols and where required for targeted axillary dissection. Where the sentinel node shows evidence of involvement (micro or macrometastases) further treatment should be according to local and national protocols and can include monitoring, completion axillary clearance or radiotherapy.

## 9.11. Histopathology

Diagnostic, post-surgical and further surgery histopathology data will be collected on dedicated CRFs. We have used the fields recommended in the RCPath dataset for histopathological reporting of breast cancer

EndoNET\_Protocol\_V4.0\_21Aug2024

© Copyright: The University of Oxford and Oxford University Hospitals NHS Foundation Trust 2022 Page 49 of 84

surgical resections as score cancer minimum dataset fields (https://www.rcpath.org/uploads/assets/7763be1c-d330-40e8-95d08f955752792a/G148\_BreastDataset-hires-Jun16.pdf).

## 9.12. Radiotherapy

#### 9.12.1. Breast Radiotherapy

Radiotherapy, where required, should be given according to local protocols and national guidance. Consistent with NICE NG101 guidance for neo-adjuvant chemotherapy, both pre-treatment imaging findings as well as post-surgical histology should be considered in radiotherapy decision making in patients allocated to NET. Partial breast radiotherapy can be considered following breast conservation where tumour size is 3 cm or less on imaging at presentation and final histology. We note the recent adoption of a 5 fraction regimens nationally. The same radiotherapy fractionation protocol should be used for patients in both arms of the trial in individual centres.

Radiotherapy data will be collected on a dedicated CRF and will include information on whether the participant received radiotherapy, the type of radiotherapy and dosage. Further information related to the details of the radiotherapy given will also be recorded.

## 9.13. Subsequent Follow Up Visits

All follow-up visits in the standard of care comparator arm are in line with routine clinical practice with surgery by 2-4 weeks (up to 8 weeks permitted for trial purposes), as per NHS treatment targets.

In the NET arm, there are additional visits for USS with core biopsy and marker clip at 2-4 weeks and for USS and clinical assessment at 3 months and 5 months. Assessment timings are designed to correspond to routine care visits and ensure that, wherever possible, patients are assessed at comparable timepoints in the care-pathway in both arms.

Participants will complete questionnaires electronically and be emailed HRQoL and Health Care use questionnaires via REDCap at baseline, 2-4 weeks, 6 weeks, 5 months, 7 and 15 months, with an option to be contacted by the Surgical Intervention Trials Unit (SITU) by posted letter with a paper version of the questionnaires, if the participant expresses this as their preference. Participants may be contacted by telephone for any outstanding PROMs/questionnaires. In some circumstances, where it is not feasible to complete questionnaires using our preferred method(s), participants may complete questionnaires over the telephone. This may be due to a patient being located in a remote geographical location. Participants may be contacted by the central trial team to query any overdue data.

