#### 5.2. Quality of Life in Breast Cancer Survivors

Very little is published about the impact of NET on HRQoL and we were unable to identify any studies that evaluated HRQoL in those receiving surgery followed by endocrine therapy in comparison with NET and surgery. One study of primary hormone therapy (endocrine therapy without subsequent surgery) (36) demonstrated a small benefit at 3 months from the omission of surgery, but scores were similar at 2 years. A single arm sub-study of neoadjuvant AI suggested that neoadjuvant letrozole did not impact on global QoL but letrozole did increase endocrine side effects (37). Extrapolation from studies including randomised trials in the adjuvant setting, demonstrate a negative impact of ET on HRQoL (38, 39) which is worst at 3 months and stabilises thereafter (38), but improves post completion of treatment (40). Since both arms of our proposed study are designed to start ET at randomisation and therefore receive ET for the same total duration during the study (from study entry to month 15), we would anticipate that although the ET impacts on HRQoL, this would be similar in the two arms.

The evidence that BCS leads to improved body image and psycho-sexual functioning is consistent across studies for surgical type (mastectomy vs BCS) (41, 42), and are independent of age (43). The effects on physical functioning and global HRQoL improve with time and predominantly in the first 2 years, whilst in

EndoNET\_Protocol\_V4.0\_21Aug2024

© Copyright: The University of Oxford and Oxford University Hospitals NHS Foundation Trust 2022 Page 23 of 84 contrast the effects of mastectomy on body image and sexual functioning, less readily improve with time (44).

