#### 6.2 Primary and secondary outcome measures

2	. To evaluate tumour response rates following NET 	2.	Response rates according to RECIST (USS, clinical, relative to baseline); MRI where used as part of local unit centre policy	2.	2-4 weeks, 3 and 5 months post- randomisation (NET arm)
3	
 
To compare invasive tumour size, histological grade and lymph node status (including number of involved nodes) in both arms
 
	3.	Tumour size, histological grade and lymph node status pre-surgery and final histology post-surgery	3.	Pre and post- operative
4		4.	Patient reported outcomes as measured by FACT-B (with ES and +4), Breast-Q, Hopwood Body Image Scale and EQ-5D-5L	4.	Baseline, 6 weeks or post-operative, 5, 7, and 15 months post- randomisation 
5		5.	Pre-operative Endocrine Prognostic Index (PEPI) score	5.	Baseline sample, 2-4 week sample and post- operative sample
6	To compare post-surgical complications and AI side effects in both arms 	6.	Post-surgical complications, side effects; delays to commencement of subsequent treatment	6.	2-4 and 6 weeks, 3 months, 5, 7, 12 and 15 months post- randomisation
7		7.	Treatment Compliance and rates of cross-over	7.	2-4 weeks, 5 months and 15 months post- randomisation.
8	. To evaluate the prognostic significance of Ki67 	8.	Ki67 % in tumour cells, % reduction in Ki67 from baseline to biopsy or surgery	8.	Baseline (both arms) and after 2- 4 weeks of AI (in both arms) and at surgery (in comparator arm);

9. To assess the surgical and locoregional management of the breast 	9. Rates of re-excision and further surgery after BCS; specimen weight after BCS; requirement for advanced BCS (therapeutic mammoplasty and local perforator flaps), rate of reconstruction	9. Baseline, post- operative, 15 months post- randomisation
10. To assess the surgical and locoregional management of the axilla 	postmastectomy, breast radiotherapy 10. Rates of sentinel node biopsy, axillary clearance, axillary radiotherapy	10. Baseline, post- operative, 15 months post- randomisation
11. To compare rates of local and distant recurrence 	11. Rates of local and distant recurrence	
 
11. 15 months post- randomisation, and periodically for long term follow up 
 

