## 9.2. Schedule of trial procedures (Main Trial)

All follow-up visits in the standard of care comparator arm are designed to be in line with routine clinical practice with surgery by 31 days, as per NHS treatment targets (if this target is not met due to any local logistical or practical reason, the protocol will allow a window of up to 8 weeks, and therefore first surgery within 8 weeks does not constitute a protocol deviation). In the NET arm there are additional (excess treatment visits) for USS with core biopsy and marker clip at 2-4 weeks and for USS and clinical assessment at 3 months and 5 months. Assessment timings are designed to correspond to routine care visits and ensure that, wherever possible, participants are assessed at comparable timepoints in the care-pathway in both arms.

Participants will complete questionnaires electronically and be emailed links to complete HRQoL and Health Care-use questionnaires via the trial database of REDCap at baseline (pre-randomisation), 2-4 weeks, 6 weeks, 5 months, 7 and 15 months, with an option to be contacted by the Surgical Intervention Trials Unit (SITU) by posted letter with a paper version of the questionnaires, if the participant expresses this as their preference. In some circumstances, participants may complete questionnaires by telephone. The trial team may also contact participants by telephone if questionnaires are overdue or to query missing data, and this will be limited to two contacts before no further reminders or queries are made.

EndoNET\_Protocol\_V4.0\_21Aug2024

© Copyright: The University of Oxford and Oxford University Hospitals NHS Foundation Trust 2022 Page 38 of 84

Randomisation       Randomisation       X       X       X       X       X       X	X X 2-4 Weeks (up 2-4 Weeks (u	1 month) N           X           X           X           1 month) N           1 month) N           6 Months (+/-           1 month) N	X X 7 Months (+/-	12 Months           12 Months           14/-1 month)           (+/-1 month)
X		X		x x x x x x
X		X		x x x x x x
X		X		x x x x x x
X		X		x x x x x x
X	X			x x x
X	X	X		X X
X	X	x		X
		X	X	
x	x	×		x
X				
x				
x				
	x			
	x		Xc	XN
	X	N XN		
	Xc	XN		
	X N X N	N XN		
	X N			
X (SAEs related to the AI treatment are reportable until surgery as defined in Section 11.8)				
	x x x *	N X  X N	X 	X X4

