## 11.5. Reporting side effects in relation to IMP treatment

Side effects frequently experienced by patients undergoing AI therapy for breast cancer are collected as outcomes in the trial's CRF for the duration of patient participation in the trial (15-months for both arms) and include the following:

- Vasomotor including hot flashes/flushes and night sweats/hyperhidrosis
- Musculoskeletal including myalgia and arthralgia/joint pain;
- Central nervous system including nausea, vomiting, and fatigue;
- Urogenital including vaginal haemorrhage/bleeding, vaginal dryness and urinary tract infection;
- Gastrointestinal including anorexia;
- Other including alopecia.

Generally, these are mainly mild or moderate in nature, and most are associated with oestrogen deprivation.

The above events must also be reported as SAEs if they meet the definition of serious and occur during the trial's defined safety reporting window.

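### Aromatase inhibitor (AI) side effects are compared between arms at 3 and 5 months, but the visit text gives clinical assessments then to NET only, so recorded rates may be inflated in NET

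*Protocol*

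**What the plan says.** Section 6.2, secondary objective 6, is comparative: "To compare post-surgical complications and AI side effects in both arms". Its timepoints, not split by arm, are "2-4 and 6 weeks, 3 months, 5, 7, 12 and 15 months" after randomisation, and its footnote marks the outcome as measured in both arms. Section 11.5 has the common AI side effects (hot flushes, joint pain, fatigue and others) collected on the CRF "for the duration of patient participation in the trial (15-months for both arms").

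The visit text is not symmetric. Section 9.2 states: "In the NET arm there are additional (excess treatment visits) for USS with core biopsy and marker clip at 2-4 weeks", and continues with ultrasound and clinical assessment at 3 and 5 months. Section 9.13 repeats this as "USS and clinical assessment at 3 months and 5 months" for NET. Both sections describe control follow-up as routine practice. Table 1 in section 5.2 lists close monitoring for six months as a feature of NET and lighter follow-up after surgery as a feature of control. Section 9.13 nevertheless aims that, wherever possible, "patients are assessed at comparable timepoints in the care-pathway in both arms".

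Questionnaires go out at baseline, 2-4 weeks, 6 weeks, 5, 7 and 15 months (sections 9.2 and 9.13). FACT-ES, the patient-reported endocrine scale, is given at baseline, 6 weeks, 5 and 15 months in both arms (footnote 3 to Table 2).

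**The concern.** Both arms start an AI at trial entry and take it for the same total time. Section 5.2 accordingly expects no material difference: "we would anticipate that although the ET impacts on HRQoL, this would be similar in the two arms". A between-arm difference in recorded side effects would therefore be read as a cost of NET.

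Recorded side effects depend on how often and in what way women are asked. If NET participants sit in front of a clinician at 3 and 5 months and control participants do not, the NET form can fill faster with identical true toxicity. Section 9.7 says blinding is not possible, so knowledge of allocation can add to this. Section 12.2 tests binary secondary endpoints by chi-squared with a relative risk, and section 12.6 sets p<0.05 without adjustment for multiplicity, so a modest artefact could be reported as significant.

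Serious adverse event reporting cannot act as a balanced check. Its window closes at surgery (section 11.8), which is up to 8 weeks in control and about 6 months in NET. The CRF is the clinical-record measure that spans 15 months in both arms, so its collection needs to be symmetric.

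**Working it through.** **Step 1. Set the readable schedule side by side.**

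| Outcome 6 timepoint | Clinical contact named, NET | Clinical contact named, control | Questionnaire, both arms |
|---|---|---|---|
| 2-4 weeks | biopsy and clip visit | surgery target | yes (not FACT-ES) |
| 3 months | clinical assessment and ultrasound | none beyond routine care | none |
| 5 months | clinical assessment and ultrasound | none beyond routine care | yes, with FACT-ES |

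At 2-4 weeks both arms have a contact, so this timepoint shows no excess in NET. At 5 months FACT-ES gives a symmetric patient-reported measure. At 3 months the readable text names a clinical contact in NET only and no patient-reported measure in either arm.

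**Step 2. Sample size, to obtain the evaluable number per arm.** The point disputes no figure in the protocol. From section 12.3: 55% versus 65%, two-sided 5%, 5% loss.

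n = [1.96·√(2·0.60·0.40) + z·√(0.55·0.45 + 0.65·0.35)]² / 0.10²

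- 80% power: 376 per arm; 376/0.95 gives 396; total 792. Matches.
- 90% power: 503 per arm; 503/0.95 gives 530; total 1060. Matches.

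**Step 3. Illustrate how unequal occasions could act.** Assume each occasion independently records a given side effect with probability q, equal in both arms. The chance of at least one record over k occasions is 1 − (1 − q)^k. The protocol gives no q, so a range is shown. The last column is the chance that a two-sided 5% two-proportion test rejects with 376 per arm.

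| q | Occasions, NET v control | Ever recorded | Relative risk | Rejects |
|---|---|---|---|---|
| 0.03 | 7 v 5 | 19.2% v 14.1% | 1.36 | 46% |
| 0.10 | 7 v 5 | 52.2% v 41.0% | 1.27 | 87% |
| 0.30 | 7 v 5 | 91.8% v 83.2% | 1.10 | 95% |
| 0.03 | 7 v 6 | 19.2% v 16.7% | 1.15 | 15% |
| 0.10 | 7 v 6 | 52.2% v 46.9% | 1.11 | 31% |
| 0.30 | 7 v 6 | 91.8% v 88.2% | 1.04 | 36% |
| any | 7 v 7 | equal | 1.00 | 5% (nominal) |

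The 7 v 5 rows suppose that control has no record at 3 or 5 months; the 7 v 6 rows suppose that only the 3-month record is missing.

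**Step 4. Relax independence.** Hot flushes and joint pain tend to persist. Suppose instead that 40% of women have a persistent symptom and each occasion detects it with probability d. Ever recorded is then 0.40·[1 − (1 − d)^k].

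- d = 0.3: 36.7% (k = 7) v 33.3% (k = 5), a gap of 3.4 points.
- d = 0.5: 39.7% v 38.8%, a gap of 0.9 points.
- d = 0.7: 40.0% v 39.9%, a gap of 0.1 points.

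The artefact therefore runs from nil to about 12 points (at q = 0.20 with 7 v 5 occasions, 79.0% v 67.2%), depending wholly on assumptions that the protocol does not settle.

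**The case against.** A reader might infer that control has no side-effect assessment at 3 and 5 months and that NET is bound to look more toxic. The documents do not support that.

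- Outcome 6 is footnoted as measured in both arms, and section 11.5 covers both arms for 15 months. Sections 9.2 and 9.13 describe the extra NET visits without mentioning side effects.
- The schedule table in 9.2 is broken in the text available and the schema in 7.2 is missing. The schema's caption says that it shows measurement timepoints and care visits for both arms and that some appointments are by telephone. Either could show a control contact at 3 or 5 months.
- Section 11.5 does not say that a clinician fills in the side-effect form. The compliance form in 10.1.3, also called a CRF, is based on a patient questionnaire.
- FACT-ES already gives a symmetric comparison at 5 months.
- No endpoint of the ever-recorded kind is stated. Outcome 6 is listed by timepoint, and detail is left to a statistical analysis plan that is not at hand.

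All of this stands, and it rules out any claim of certainty or a fixed size. It does not remove the gap. The visit text gives extra clinical contact to one arm of an open-label trial at two of the comparison timepoints, and no readable passage secures matching collection in control. At 3 months nothing patient-reported stands beside it. Even if both arms complete the form at all seven timepoints, a difference in mode, such as clinic against telephone, could remain.

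**Conclusion.** The point holds as a risk of differential ascertainment. It is strongest at 3 months and weaker at 5 months, where FACT-ES covers both arms. Recorded AI side effects may be inflated in NET although exposure is the same.

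The size cannot be derived from the protocol. The figures in the working rest on an assumed recording probability, assumed numbers of control occasions and an ever-recorded endpoint, and they shrink to between 0.1 and 3.4 points under the persistent-symptom assumption. A reader might take the 7 v 5 rows as the expected bias, but they are the case in which control is not asked at all at 3 and 5 months, which the protocol does not say. The number-of-occasions artefact is zero if both arms complete the same form at all seven timepoints. The primary endpoint and the sample size are unaffected.

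**What to change.** **Option 1, wording only.** Name FACT-ES at 6 weeks, 5 and 15 months as the main between-arm comparison of endocrine side effects. Restrict any formal comparison of CRF side effects to timepoints where both arms are asked with the same form and mode, and state which those are; the readable text does not show that any particular set qualifies. Report findings from NET-only visits descriptively. When interpreting the 6-week FACT-ES, note that control will typically be post-operative and NET will not. Cost: the clinic-based 3-month contrast is lost. This option also works for participants already enrolled.

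**Option 2, a small addition to data collection.** Send both arms one identical side-effect checklist through the existing REDCap route at 3 and 5 months, and base the comparison at those timepoints on it rather than on clinic reports. Cost: one short extra electronic form per participant at each of these timepoints, and an amendment. This keeps the 3-month contrast.

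If the schedule already has both arms completing the same form in the same way at all seven timepoints, one sentence in section 9.13 or 11.5 saying so would close most of the gap.
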